implement in older children even for a six week period. It moreover delays speech and has palatability issues (10). In real-life, the option of an elementary diet in Belgium after weaning is seldom discussed, as EoE unfortunately still forms no basis for reimbursement of the very expensive AA diet (although a reimbursement procedure has recently been started)(10).

- b) Empiric elimination of common dietary antigens. This diet is usually referred to as “6-food, 4-food, 2-food or 1-food” diet :

6 food : cow’s milk, soy, eggs, wheat, nuts and fish; 4 food : cow’s milk, eggs, wheat, soy; 2 food : cow’s milk and wheat & 1 food : cow’s milk (9, 10). A step-down or step-up approach for these empiric eliminations can be used. When a step-down treatment is chosen, the patient will first eliminate all foods, after which (if remission is obtained), new food products will be gradually introduced and 8 weeks after the introduction of each new food product, a gastroscopy with biopsy will be done to check for the maintenance of remission. If EoE re-occurs, the newly introduced food product is causal and will be permanently eliminated. If the step-up approach is chosen, a single food product is eliminated and if no remission is visualized on biopsy 8 weeks after elimination, an additional food product will be eliminated until remission is obtained and those foods will be eliminated permanently. More specifically:

 - a. Step-down treatment starts as an 8 weeks 6-food diet after which a new biopsy is needed to prove remission. After this initial remission the diet is reduced with one specific food rationally chosen by the caregiver, the parents and the child for 8 weeks after which a new biopsy needs to prove whether or not the newly introduced food can stay in the diet or has to be removed again. This has to be repeated for each food product that will be reintroduced. As such, the diet starts with a high level of restrictions, has long diagnostic procedures and requires a high number of endoscopies. A new guideline tries to reduce the initial diet by starting from a 4 food diet instead, as nuts/peanuts and fish/shell-fish is only responsible for a limited number of cases (5)

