b. Step-up treatment starts as an 8 week diet on cow's milk alone after which a new biopsy is taken to study remission. If remission is obtained (RR 33% in children), the patient remains on a cow's milk free diet. However, if there is no remission, a second food product needs to be eliminated. This in general might reduce the number of biopsies needed, but in children in whom after multiple weeks of limited and later-on very limited food product allowed, still no remission is obtained, the psychological barrier to add another food product to the forbidden list, which the chance of (again) failure to obtain remission, is an extreme burden.

c) Allergy-driven Food Elimination

Using allergy testing-guided food elimination in children results in a success rate in children that is slightly higher than the success rate of a 2-food elimination diet, but is lower than its rate with a 4-food elimination diet (2, 10). Its use is certainly more recommended in children when compared to adults in whom allergy-driven food elimination has a low success rate.

In UZ Leuven if parents, children and treating physician agree on option 2 (diet-driven treatment), in infants and pre-school children it is advised to start with a 1-food diet (milk) and if unsuccessful (after 8 weeks diet new biopsy shows no remission) a step-up protocol to a 4-food diet (milk, eggs, wheat and soy) is advised. As in Belgium soy intake in infants is usually limited, for the large majority of young infants and pre-school children this de facto means a 3-food diet (milk, eggs and wheat). In school-children and adolescents, children are advised to start with a 2-food or 4-food diet (depending on their willingness to adhere to the protocol) and to step-up to a 6-food diet immediately when after 8 weeks of initial diet no remission was obtained. Allergy testing usually occurs to rule out (associated) typical IgE mediated food allergy and/or pollen-associated risk factors with the chance of increased number of eosinophils in the esophagus during the pollen season and in this case, biopsies will not be taken during the pollen season.

However, whereas in IgE-mediated pediatric food allergy recent evidence exists that heat-denaturation of proteins might reduce their allergenicity and could lead to symptomfree introduction of certain recipes, nothing is known about the impact of heat denaturation on food proteins in pedEoE. Indeed, for several decades, it is known that food allergic

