The objective of the study is to study whether the introduction of heated food products (more specifically heated hen's egg and/or cow's milk) in children with EoE would be possible without re-occurrence of the eosinophilic inflammation, while the intake of less heated products might cause disease recidive. Moreover, we would like to study whether the gradual re-introduction of less heated products after the most heated form is tolerated, could lead to tolerance induction in EoE.

Primary end-point:

- Primary end-point of the study is to study the number of ped EoE children by inclusion on hen's egg and/or cow's milk free diet with potential remaining remission (<15 eosinophils/hpf on esophageal biopsies) after 8 weeks (re)introduction of heat-denatured hen's egg and/or cow's milk proteins (introduced sequentially as on the one hand baked egg (cake), hard-boiled egg, omelet and soft-boiled egg and on the other hand 20' cooked cow's milk, 15', 10' and 5' cooked cow's milk).

Secondary end-points:

- The number of pedEoE children in whom remission remain with introduction of cake and/or 20'cooked cow's milk (step 1), but no longer with less heated proteins
- To study whether remission is associated with specific circulating and/or local food protein IgG4 reduction (when baseline levels (serum) would be (stored) available) (and increase upon unsuccessful introduction of less heated proteins)
- To study whether remission could be associated with changes in local IgG4 production (on biopsy staining)
- To study whether we could develop an *in vitro* mimicking B cell activation test by stimulating PBMC with food proteins obtained after different heat-denaturating steps
- Can we observe a correlation between Pediatric EoE PEES v2.0 and Peds-QL scores (obtained in all ped EoE children participating in study s64441) and histologic remission?
- To study the presence of associated atopy (tree-, grass- or weed pollen or fungi allergy)
- To study the presence of associated typical IgE mediated food allergy (sensitization and documented symptoms)

Material and methods

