- *Inclusion criterion:* All children (aged 12 months and older) presenting (since 1-1-2014: moment of diagnostic guideline standardization for pedEoE) with diagnosed pedEoE at UZ Leuven eliminating either hen's egg or cow's milk or both and in complete remission after their latest biopsy (no longer than 12 months earlier, but preferentially as short as possible after their latest biopsy) are eligible for the study. If the last biopsy has been performed more than 12 months earlier, a new gastro-duodenoscopy will be performed to verify remission and rule out e.g. active gastritis. If they are on PPI and/or local budesonide treatment, this should be stable for at least 3 months and will remain untouched during the entire study. We will include 18 pedEoE subjects in total.
- *Exclusion criteria:*
 - Children younger than 12 months
 - Children with active pedEoE
 - Children who refuse to adhere to the protocol
 - Children with associated IgE mediated hen's egg and/or cow's milk allergy with specific IgE antibody titers that predict active (baked egg and/or baked milk) food allergy with cut-off titers as used at the consultation of allergy (KLL). Those children will become eligible however if their titers decrease while the study is still open.

Study design:

Study subjects and study procedure

If inclusion criteria are met, after obtaining informed consent from the parents (and when old enough, assent from the children) 18 children will be included in this pilot pedEoE trial.

Children will be provoked in-house (UZ Leuven petit-cru), based on the written procedure available for heated egg (wheat or rice flour based) or cow's milk provocation. If on diet for both, parents and children will decide which allergen they will start with, but both food products will be introduced sequentially in time (this is after complete termination of the first food introduction). Afterwards, they will introduce heated egg by cake or 20' boiled cow's milk at least three times a week for 8 weeks (as for the TETI study (10)) and will return to the hospital for a gastroscopy with biopsies. EoE remission will be studied on 2X3 biopsies

(upper and lower esophagus) by eosinophil staining within the routine anatomopathological laboratory within our hospital.

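### Entry and endpoints ignore whether the tested food is a proven trigger, so a child who never relapses cannot be counted as tolerance induction or, without the raw/UHT step, as heat-tolerant

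*Protocol*

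**What the plan says.** **Entry.** The inclusion criterion in the Protocol (Material and methods) takes children "with diagnosed pedEoE at UZ Leuven eliminating either hen's egg or cow's milk or both and in complete remission after their latest biopsy". Neither it nor the exclusion criteria ask for evidence that the food to be tested drives the disease in that child.

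**The protocol's own test.** The background text on step-down diets states how a trigger is recognised: "If EoE re-occurs, the newly introduced food product is causal and will be permanently eliminated".

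**How foods come to be eliminated.** The two smallest empiric diets do not contain egg: "2 food : cow’s milk and wheat & 1 food : cow’s milk". In the youngest children at UZ Leuven, if removing milk alone fails, "a step-up protocol to a 4-food diet (milk, eggs, wheat and soy) is advised". Because little soy is eaten at that age, "this de facto means a 3-food diet (milk, eggs and wheat"). Older children start on two or four foods and step up to six.

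**Objectives and endpoints.** The Primary end-point counts children who stay below 15 eosinophils/hpf after 8 weeks of a heated food, "introduced sequentially as on the one hand baked egg (cake), hard-boiled egg, omelet and soft-boiled egg", with four boiling times for milk in parallel. The first secondary endpoint counts children who keep remission at step 1 and lose it on less heated food. Study objectives also asks "whether the gradual re-introduction of less heated products after the most heated form is tolerated, could lead to tolerance induction in EoE". None of these refers to trigger status.

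**Last step.** Children who tolerate step 4 may stop or, as an option, try raw egg or uncooked UHT milk. The Statistical analysis section expects most children to start with egg.

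**The concern.** A child can be avoiding egg or milk that never caused the disease. Such a child stays in remission whatever form of the food is given, and so produces the same record as a treatment success. The natural evidence for tolerance induction is kept remission through all steps, which is exactly what a never-reactive child shows.

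The protocol's own reasoning presumes a trigger. It anticipates relapse at the raw step, and its clinical precedent is a single boy whose disease was driven by milk. At stake is attribution: kept remission could be reported as heat tolerance or induced tolerance in a child for whom the food was irrelevant.

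**Working it through.** **1. What each route to elimination says about the food** (background text, Option 2)

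| Route | Trigger evidence |
|---|---|
| Milk removed alone, remission | Points to milk (remission rate in children given as 33%) |
| Two foods, remission | Milk not separated from wheat |
| Milk fails, then four foods (in practice milk, egg, wheat) | Egg is a leading candidate, not separated from wheat |
| Four or six foods, remission | No single food identified |
| Step-down, biopsy relapse on reintroduction | Food is causal by the protocol's own test |
| Allergy-test-guided elimination | May point to a food; no biopsy relapse on eating it is required |

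The general step-up description adds one food at a time, which would be more informative, but the local practice for the youngest goes from one food to four. In every listed empiric diet that contains egg, other foods are removed with it.

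**2. What each type of child shows in the trial**

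| Type of child | Steps 1 to 4 | Raw/UHT, if taken |
|---|---|---|
| Never reactive to the food | Kept | Kept |
| Newly tolerant | Kept | Kept |
| Tolerates all four heated forms only | Kept | Relapse |
| Tolerates only the more heated forms | Kept, then lost | Not reached |

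The raw/UHT step separates the third type from the first two. It cannot separate the first from the second. A child who stops after step 4 may be any of the first three.

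**3. Size, as an illustration**

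Inputs: n = 18 (Inclusion criterion, Study subjects and study procedure, Statistical analysis; the background text once says 8). q is the share of enrolled children whose tested food is not a trigger. The documents give no figure, so q is assumed. Also assumed: no heat effect, no induction, relapse visible within 8 weeks, and no relapse from other causes.

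- Expected number kept at every step = 18q.
- P(at least 4 kept) is the binomial upper tail with n = 18 and probability q.

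| q | Expected kept | P(at least 4 kept) |
|---|---|---|
| 5% | 18 × 0.05 = 0.9 | 0.01 |
| 10% | 18 × 0.10 = 1.8 | 0.10 |
| 20% | 18 × 0.20 = 3.6 | 0.50 |

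A much larger assumed share, q = 50%, would give 9.0.

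**4. Effect on a step 1 share**

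If h is the share of true-trigger children who tolerate step 1, the observed share is q + (1 − q)h. For an observed 9 of 18 (0.5), h = (0.5 − q)/(1 − q):

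- q = 5%: 0.45/0.95 = 47%
- q = 10%: 0.40/0.90 = 44%
- q = 20%: 0.30/0.80 = 38%

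Over this range the distortion at step 1 is modest. The main problem lies with children who never relapse.

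The protocol plans no test and derives no sample size, so there is no stated figure to reproduce.

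**The case against.** **It is a descriptive pilot, and no endpoint counts tolerance induction.** The protocol says it has no indication that induction occurs in EoE and only hopes for it. This limits the consequence to how results are worded. But induction is a stated objective, and a descriptive report still needs a label for the child who completes every step.

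**Reporting by subgroup and chart items belong in the SAP or the case report form.** Partly right, and their absence from the protocol is not the complaint. The point rests on what the protocol does fix: an entry rule and an objective that do not fit together. An SAP can stratify by trigger status only if that status is collected.

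**Some children will already have trigger evidence.** True, through step-down relapse or remission on removing milk alone. This makes the fix feasible.

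**A child who relapses later has shown that the food matters.** Largely so, which is why the first secondary endpoint remains useful. A reader might go further and infer that non-trigger children can never enter that endpoint. The documents do not support this: the background text says esophageal eosinophils may rise in the pollen season and that clinic biopsies then avoid it. The study biopsies at T8, T17, T26 and T35 span seasons, and the study procedure does not repeat that precaution.

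**The share q has no documentary basis.** Correct. The figures illustrate scale and estimate nothing.

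**Conclusion.** The point stands as a mismatch between the entry rule and the tolerance objective, and should be fixed. For a child with an unproven trigger who never relapses, the trial cannot tell new tolerance from no reactivity; if that child stops after step 4, it cannot exclude tolerance of heated food only either. This follows from the design and does not depend on q. Only the number of children affected does: 0.9, 1.8 or 3.6 of 18 expected at an assumed 5%, 10% or 20%, under the assumptions listed above.

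Three stronger readings are tempting and not supported:

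- *All three classes are confused in every child who completes the trial.* A child who tolerates only heated food would be expected to relapse at the raw/UHT step, so for those who take it only two classes remain confused.
- *The primary endpoint is invalid.* It asks whether heated food can be introduced without losing remission, and a kept remission answers that whatever the reason.
- *The all-18 stopping rule is defective for this reason.* One non-trigger child prevents it from being met, but so does any single kept remission from any cause.

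**What to change.** 1. At V0, record from the chart, for each tested food, whether it is a proven trigger (biopsy-documented relapse when eaten, or remission on removing that food alone) or unproven. Use evidence from before entry only.
2. Report the primary count per step, by food and by this pre-entry status.
3. Give any share of children who tolerate heated food only for pre-entry proven-trigger children. Report the first secondary endpoint separately as a count. Do not pool unproven children into the share because they relapsed in the trial, since that selects on the outcome. Note that a late relapse may have another cause, such as the pollen season.
4. Label an unproven child who never relapses *non-trigger or tolerant*, and do not count that child as tolerance induction. If too few proven-trigger children are enrolled, limit the conclusion to feasibility of introduction.

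**Cost.** Protocol wording and a chart review at V0. Eligibility, treatment, procedures and the stopping rule do not change. The price is small strata, probably smallest for proven egg triggers, and wide intervals. For an observed 50%, the exact (Clopper-Pearson) 95% interval is 26-74% for 9 of 18, 21-79% for 6 of 12, 12-88% for 3 of 6 and 7-93% for 2 of 4.

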Presenting **symptoms** in children are different depending on the age of manifestation and are listed in figure 2A and 2B and Figure 3 (3, 4). Typical food impaction, as observed in adults with EoE, can be the presenting symptom in adolescents, but is seldom a symptom in young

children in whom vomiting, chronic nausea and feeding problems might be more frequent. Children develop spontaneous coping mechanisms to live with the disease, such as drinking a lot of fluids during meals, being unable to eat unless a drink is available, chew the food for a long time and/or cut the food in small pieces (3).

A

Common symptoms of eosinophilic esophagitis

Younger Children

Older Children and Adolescents

Vomiting	Epigastric pain
Chronic nausea	Dysphagia
Regurgitation	Nighttime cough
Irritability/feeding difficulties	Food impaction

Figure 2 A and B:

Typical symptoms in children with EoE depending on age of presentation (3)

B

Less common symptoms of eosinophilic esophagitis

Growth failure

Hematemesis

Esophageal dysmotility

Failure to thrive

Malnutrition

[figure not shown]

Figure 3:

Spread of typical symptoms in children with EoE depending on age of presentation (4)

The disease can be **diagnosed** if in presence of typical signs and symptoms, a gastro-duodenoscopy with multiple biopsies in esophagus is performed. EoE can present macroscopically with furrowing, white mucosal plaques, esophageal trachealization, esophageal narrowing, stricture, and mucosal tearing (5). EoE is suspected when at least 15 eosinophils per high-powered field (hpf) (or 60 eos/mm²) are documented and non-EoE disorders that cause or potentially contribute to Esophageal Eosinophilia are ruled out (1, 5). Sensitivity of 100% and specificity of 96% can be obtained if the number of proximal and distal biopsies in the esophagus is increased to 2-4 biopsies proximal and distal. Therefore this number is currently recommended for successful diagnosis (5). Similarly, remission is defined as < 15 eosinophils per high-powered field and also requires 2-4 biopsies both in proximal and distal esophagus (5)

Risk factors for the disease are represented in figure 4.

Risk factor	Comment
Aeroallergens	Might cause EoE or increase disease activity; can cross react with food allergens; may explain seasonal variation in diagnosis

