Treatment guidelines now uniformly advise the use of high-dose proton-pump inhibitors (PPI) as first treatment line for 8 weeks, after which a new biopsy is recommended to search for remission (7). If the patient is in remission (eosinophils <5/hpf), long-term PPI (1 mg/kg/d) treatment is recommended and continued as long as yearly biopsies remain negative (and hence might be lifelong). On the other hand, if a patient is not yet in remission (eosinophils > 15/hpf), or only has partial remission (eosinophils 5-15/hpf), a second treatment line is initiated. For this second treatment line, parents and children in accordance with their treating physician have two different options: 1) to start a treatment with local corticosteroids or 2) to start a treatment with food elimination diet.

1) Option 1: use of local corticosteroids:

- a) Swallowed corticosteroids which are highly effective (response rate (RR) 50-87 %): Fluticasone (normally used as inhaler) (110 microgram , 2-4 times/day)
- b) Budesonide (resolved in Xanthaan gum) <10 years : 1 mg; >10 years : 2 mg
- c) (in adults orodispersible Budesonide Jorveza® has recently been approved)

Patients are recommended to avoid drinking and eating for at least half an hour after administration; high RR but risk of side effects such as Infection : Candida albicans (10-15%), adrenal suppression, epithelial atrophy, growth delay (8).

In UZ Leuven, if parents/children and treating physician agree on the use of option 1, treatment with local corticosteroids is initiated as Budesonide in Xanthaangum with subsequent biopsy to prove remission after 8 weeks treatment. If the patient is in remission, treatment is continued for at least a year till new biopsy, after which, if the patient remains in remission, sometimes a dose-reduction can be discussed. If the patient is not in remission, either an increase in the Budesonide dose or switch to option 2 will be discussed. Alternatively, the continuation of Budesonide with the start of a restriction diet in parallel can be discussed.

2) Option 2: use of diet (We recently published the remission rates for each of these diets based on meta-analysis (10).)

- a) Elementary diet (amino-acid (AA)) diet. First publication by Kelly *et al* in 1995); RR in children 90%-95%; duration minimum 6 weeks; clinical improvement observed after 8,5 ± 3,8 days, histological remission in 2 weeks (9). However, the diet is highly restrictive and almost impossible to

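### Does it matter that entry asks for complete remission without giving an eosinophil count?

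*Protocol*

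**What the plan says.** Under Material and methods, the inclusion criterion admits children who eliminate hen's egg, cow's milk or both and are "in complete remission after their latest biopsy". If that biopsy is more than 12 months old, "a new gastro-duodenoscopy will be performed to verify remission". The exclusion list adds "Children with active pedEoE". None of the three carries a count.

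Counts appear in three other places:

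- Background text on diagnosis: "remission is defined as < 15 eosinophils per high-powered field", and on the other side of the same line, "EoE is suspected when at least 15 eosinophils per high-powered field".
- Background text on treatment guidelines after proton-pump inhibitors: "If the patient is in remission (eosinophils <5/hpf" per field, and "if a patient is not yet in remission (eosinophils > 15/hpf), or only has partial remission (eosinophils 5-15/hpf" per field.
- Primary end-point: "remaining remission (<15 eosinophils/hpf on esophageal biopsies", assessed after 8 weeks of the heated food.

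The Statistical analysis section foresees mainly descriptive reporting and no testing. The planned number of children is 18.

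**The concern.** The entry term is not defined, and the document prints two scales that could define it. A child at 5 to 14 is in remission on the diagnostic scale and only in partial remission on the treatment scale. Two investigators could screen the same child differently and both point to the text.

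The end-point counts children whose remission remains, which suggests that the entry state was kept. If entry means below 5, a child who rises to 5 to 14 is still a success, although the treatment scale would call that partial. If entry means below 15, a child may already start at 5 to 14. In a small single-group study these could look like different results under one label. The rule for going on to the second food after lost remission speaks only of remission, so it might also seem that the two foods could start from different states.

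**Working it through.** The protocol gives no figure to reproduce, since there is no test, power statement or target rate. The check is to place each count on each printed scale and ask whether the primary result depends on the entry reading.

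| Eosinophils per field | Diagnostic scale | Treatment scale | Entry if limit is <15 | Entry if limit is <5 | Primary end-point if seen after the food |
|---|---|---|---|---|---|
| 0 to 4 | remission | remission | yes | yes | remission |
| 5 to 14 | remission | partial | yes | no | remission |
| exactly 15 | EoE suspected | partial | no | no | not remission |
| above 15 | EoE suspected | not in remission | no | no | not remission |

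1. **The disputed band at entry is 5 to 14.** Exactly 15 is labelled differently by the two scales, but neither entry reading admits it, and the end-point's strict limit settles it for the result.
2. **Every entrant is below 15.** This is immediate if the entry limit is 15. If the limit is 5, it follows because a count below 5 is also below 15. So on either reading no child enters on the failure side of the end-point.
3. **The end-point column uses only the count after the food.** A child at 5 to 14 after step 1 counts as in remission whether entry required below 5 or below 15. The entry reading reclassifies nobody.
4. **What can differ is who is enrolled.** Let k be the number of children at 5 to 14 who would enter under the wider reading and be replaced under the narrower one. The step 1 count can then differ by at most k, and only if each replacement has the opposite outcome. The documents do not give k. One child is 1/18 = 5.6 percentage points of the planned sample, if all 18 are assessed. If k = 0, the two readings give the same trial.
5. **Second food.** The list of study visits calls the start of the second allergen an inclusion. That supports applying the entry criterion again, though it does not prove it. In any case steps 2 and 3 hold for the second food as well.

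**The case for a change.** The best case for a change is that eligibility belongs in the protocol and is applied at screening, so a later analysis plan cannot repair it. Each reading has support. *Complete* is the natural opposite of *partial*, a grade that appears only in the treatment text, and this points to below 5. Against that, the treatment text calls below 5 simply remission, the re-check sentence in the inclusion criterion drops *complete*, and the end-point is set at below 15, which points the other way. With no control group, the starting level matters for interpretation.

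Much of this stands. The term is undefined, the two background scales disagree, and the text favours neither reading decisively.

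It does not follow that the primary result is unsound. The argument that a child at 5 to 14 after the food should be seen differently is an argument for another end-point, not about entry, and the printed end-point is explicit. Nor is the entry level the only comparison available. The first secondary end-point compares heating steps within a child, and blood markers are taken at baseline and again at each gastroscopy. A table of counts by band would be informative, but such descriptive tables are commonly left to an analysis plan, which is not shown here.

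**Conclusion.** No change to the plan is needed. The entry criterion lacks a number, but the primary count is defined by its own limit and is obtained in the same way under both readings. The effect is confined to the make-up of the enrolled group and the sense of *remaining*. Its size is unknown: at most one child in the step 1 count for each enrolled child with an entry count of 5 to 14, and nothing if there are none.

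This rests on two assumptions. One is that complete remission means one of the two printed limits, so that nobody enters at 15 or above. The other is that the latest biopsy, or the repeat one where it is over 12 months old, is the evidence used for entry.

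The two background scales do disagree in print. Reconciling them with the entry wording is an editorial matter; which count applies is a clinical decision for the sponsor, on which this review takes no position. Analysts can fill the remaining gap by describing entry counts where the pathology reports give them.
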